##### Exploratory endpoints:

- Reason for changing systemic therapy
- Choice of the next systemic therapy line
- Side effects (according to CTCAEV5 and RTOG), quality of life (EORTC QLQ-C30 prostate, QLQ-PR25, EQ-D5), assessment of organ function (gastrointestinal and urogenital: IPSS score, ICIQ-Score, NCI-PRO-CTCAE, IIEF)

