#### 3.3 In summary, the RIALTO study has the following objectives:

1. Systematic *investigation of the imaging response in PSMA-PET/CT* according to validated diagnostic criteria (RECIP or PROMISE V2) after ablative irradiation of all PSMA-PET/CT positive tumor manifestations while continuing antiandrogen therapy.
2. *Investigation of the influence of therapy on oncological parameters for all metabolically active manifestations*, as this should prolong the interval for changing systemic therapy and thus positively influence PSA levels, progression-free survival and overall survival.
3. *Assessment of the quality of life and potential side effects of radiotherapy in metastatic cancer patients* to assess the burden of the planned therapeutic intervention.  
to be able to estimate this patient cohort.
4. *In a broader sense, this study, with its research questions, prepares the ground for a randomized phase II trial for patients with unfavorable prognostic parameters, which is planned upon achievement of the primary endpoint.*

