#### 4.3.2 Radiation therapy of the prostate and metastases:

**Planned therapy:** The first radiation therapy is planned to be ultrahypofractionated prostate irradiation with 5 x 7.5 Gy on alternating days, analogous to the PACE-B trial [26], but without dose escalation to the CTV. Alternatively, if ultrahypofractionation is not possible (e.g., due to organ-risk exposure), moderate hypofractionated prostate irradiation with 20 x 3.0 Gy, analogous to the CHHiP trial [27], 20 x 2.75 Gy, or 6 x 6 Gy, analogous to STAMPEDE, can be performed.

Six months after radiation therapy to the prostate (calculated from the first day of radiation therapy), an ablative Radiation therapy for residual metabolically active metastases, preferably as stereotactic

Radiation therapy according to departmental standard (e.g., 3 x 10 Gy, 5 x 6 Gy) is planned. Alternatively, radiation therapy according to departmental standard can be performed moderately hypofractionated or normofractionated.

**Procedure:** In preparation for radiation therapy, an informational consultation is conducted, followed by a planning CT and planning MRI scan without contrast agent for treatment planning (two appointments on different days). After these preparatory examinations, radiation therapy is scheduled to begin within a maximum of 10 working days; in the meantime, treatment planning is carried out according to study guidelines.

Ultrahypofractionated prostate radiation therapy is performed under MRI guidance using an MRI/linear accelerator hybrid system, which allows for more precise soft tissue imaging than CT-guided radiation therapy. Furthermore, online adaptation of the treatment plan to the current anatomical conditions and monitoring of organ movement during radiation are possible. This allows for more precise determination of the position of organs at risk and adaptation to enable the selection of smaller safety margins (compensating for motion uncertainty as well as intra- and interfractional positioning uncertainty). This results in a lower dose to organs at risk and thus a reduction in long-term side effects. Imaging, plan adjustment, and radiation delivery take place over approximately 30 minutes.

45 minutes per radiation treatment. A total of 5 treatments of 7.25 Gy each are planned on alternating days, corresponding to a very short total treatment time of 2 weeks.

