The possible acute and long-term side effects correspond to the general side effects of radiation therapy to the pelvic region: pollakiuria, irritation of the bladder and/or urethra with irritation during urination. In the long term, a slight increase in urinary frequency and softer stool consistency may occur. Rarely, a slight deterioration in continence, more frequent urge to defecate with the occurrence of diarrhea or rectal mucus discharge may occur. In very rare cases, rectal bleeding, urinary retention with the possible need for the use of alpha-blockers with specific side effects or the need for indwelling catheterization, urethral stenosis, and, in extremely rare cases, the formation of a fistula or necrosis of the intestinal mucosa, requiring endoscopic or surgical intervention, may occur. The induction of a second malignancy cannot be ruled out (incidence of 1:100 to 1:1000 after 10 to 30 years), however, this already low risk is negligible in light of the polymetastatic prostate cancer disease.

**Specific burdens of metastasis radiotherapy:** Radiotherapy of metastases is associated with additional time commitment for appointments (3-5 for stereotactic radiotherapy; up to 25 for normofractionated radiotherapy). Depending on the number of metastases being treated, the duration of each radiotherapy session can be up to one hour. Depending on the location of the metastases, corresponding side effects from the radiotherapy may occur; however, the normal tissue constraints are chosen so that the risk of long-term side effects is 1-2%, and the focus is on maximum sparing of normal tissue. Furthermore, only metabolically active and therefore therapy-resistant metastases are treated, where further growth and thus potential complications due to local progression would be expected if no local radiotherapy or a change in systemic therapy were performed.

**Benefit of the therapy (radiation of the prostate and metastases):** The planned short-term ablative radiation therapy of metabolically active lesions, with a favorable side effect profile, aims to eliminate system therapy-resistant tumor cells in oligoresidual disease with a poor oncological prognosis. It is assumed that resistance to system therapy is driven by these resistant tumor cells. The targeted elimination of these therapy-resistant tumor cells should delay the development of resistance to system therapy, thereby extending progression-free survival and ultimately overall survival.

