#### 4.3.3 Accompanying examinations:

**Planned measures:** These will take place at the time of study enrollment/before the start of radiation therapy, in parallel with radiation therapy, at the time of completion of radiation therapy and during the follow-up.  
Study visits.

**Implementation:** Follow-up visits are planned for the following times:

1. Pre-therapeutic for study inclusion and status assessment before the start of therapy (radiation of the prostate and metastases); six (up to a maximum of 9 months) after initiation of systemic therapy with evidence of a PSA value of  $>0.2$  ng/ml.
2. At the time of completion of therapy (radiation of the prostate and metastases).  
3rd month 1, 3, 6, 9, 12, 15, 18, 21 and 24 after study enrollment.

4. Subsequently, follow-up examinations are conducted as personal visits every 3 months to 18 months after completion of metastasis-directed therapy to record PSA levels, quality of life and to inquire about possible side effects.

**Specific burdens:** Attending study visits involves a time commitment, including travel to and from the study center and the visit itself, which lasts approximately 30-45 minutes. If the PSA level is checked in the patient's outpatient setting at the time of visits not related to the discussion of PSMA-PET findings, the questionnaires can be sent by mail. In this case, approximately 30 minutes should be allocated for completing the questionnaires per visit. The PSA level is checked via blood draw, which involves venipuncture. Theoretically, this procedure carries a risk of bleeding, infection, or tissue injury. However, blood draws with PSA level checks every 3 months are already part of routine urological therapy monitoring and are not an additional measure within the study.

**Benefit:** Regular study visits ensure close monitoring with consistent, frequent check-ups of PSA levels, a surrogate parameter for cancer progression. If PSA levels rise, appropriate diagnostic procedures can be initiated immediately, and any new findings can be investigated and treated. Medical consultations and assessments of quality of life allow for the initiation of appropriate therapy in cases of quality of life limitations or the occurrence of side effects. Furthermore, patients have reported that they appreciate and value a consistent connection to their treatment center.

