## 8.3 Statistical Analysis

All planned analyses will be performed for both the ITT and PP populations. A descriptive analysis of the primary and secondary endpoints will be conducted by determining relevant statistical parameters (including mean, median, standard deviation, minimum, maximum, absolute and relative frequencies, qualitative assessment of quality of life and side effects) and calculating the corresponding 95% confidence intervals. Furthermore, a descriptive analysis of the radiation treatment plans is planned. Endpoints collected at different time points (including side effects, quality of life, and PSA levels) will be described for each time point, and their temporal progression will be visualized graphically.

For endpoints that represent an interval until an event (progression-free survival, time to change of systemic therapy, overall survival), an evaluation is also performed using Kaplan-Meier curves and log-rank tests. In addition, a Cox regression analysis is conducted to investigate potential influencing factors on the respective analyzed endpoints.

If indicated by the patients, the reasons for premature discontinuation of therapy will be investigated. In addition, the reasons for withdrawal from the program documented by the center will be reviewed.

Study and loss-to-follow-up analyzed.

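### Section 8.3 fixes a visit-by-visit description of side effects but names no per-patient toxicity summary and no time origin for each irradiation course

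*Protocol*

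**What the plan says.** Section 8.3 says of repeatedly measured endpoints: "Endpoints collected at different time points (including side effects, quality of life, and PSA levels) will be described for each time point", and adds that their course will be graphed. The same section lists, for the primary and secondary endpoints, "absolute and relative frequencies, qualitative assessment of quality of life and side effects" together with 95% confidence intervals. Section 3.2 places "Side effects (according to CTCAEV5 and RTOG), quality of life" among the exploratory endpoints. The synopsis timeline, however, refers to quality of life and side effects as secondary endpoints. Objective 3 in section 3.3 is "Assessment of the quality of life and potential side effects of radiotherapy in metastatic cancer patients".

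On timing, section 4.3.3 schedules visits at "month 1, 3, 6, 9, 12, 15, 18, 21 and 24 after study enrollment". Fig. 2 in section 7.1 carries one axis to month 36, with prostate irradiation at visit 2 and metastasis irradiation at month 6. Section 4.3.2 sets the second course at "Six months after radiation therapy to the prostate (calculated from the first day of radiation therapy").

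Two safety provisions are built differently. Section 5.6 plans a look 30 days after each course once at least 9 patients are enrolled; if grade 3 events exceed 25%, their course is checked at 90 days. The synopsis stopping rule concerns persistent grade 3 events beyond 90 days after irradiation in more than half of the patients.

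**The concern.** Section 4.3.2 names harms such as urinary retention, rectal bleeding, stenosis and fistula. Some are episodic and can strike different men at different times. A table with one row per visit shows how many men have a given grade at that visit, but not how many men ever had it. The second number is the one a reader needs in order to judge the burden of treatment under objective 3.

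The men also receive two courses about six months apart. A row defined by months on one axis corresponds to two different times since irradiation, one for each course. Without a stated origin for each course, the final report would not be on the same basis as the protocol's own safety rules.

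**Working it through.** The protocol gives no expected toxicity rate for the combined treatment, so there is no figure of the plan to reproduce on this point. The sample size of 27 is used only as a denominator.

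**1. Visit-wise prevalence against the share ever affected.** Inputs: 27 patients (section 4.4) and K = 14 visits with side-effect documentation (Fig. 2, visits 2 to 15). The per-visit prevalence p of a given grade is an assumption, as is the dependence between visits. If p is the same at every visit:

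- lower bound, the same men at every visit: p
- upper bound, different men at every visit: min(1, 14p)
- independent visits: 1 − (1 − p)^14

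| Assumed p per visit | Lower bound | Independent visits | Upper bound |
|---|---|---|---|
| 2% | 2% | 25% (about 7 of 27) | 28% |
| 1/27 = 3.7% | 3.7% | 1 − (26/27)^14 = 41% | 14/27 = 51.9% |
| 5% | 5% | 51% (about 14 of 27) | 70% |
| 10% | 10% | 77% (about 21 of 27) | 100% |

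The same visit-wise table is compatible with very different numbers of men harmed. The width of the range is the point; none of these rates is a prediction.

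**2. What each visit row contains.** Take enrolment and the start of prostate irradiation as close together, and the second course as starting at month 6. Months since the start of metastasis irradiation are then visit month − 6.

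| Visit month | Months since prostate course | Months since metastasis course |
|---|---|---|
| 1 | 1 | not yet given |
| 3 | 3 | not yet given |
| 6 | 6 | 0 |
| 9 | 9 | 3 |
| 12 | 12 | 6 |
| 18 | 18 | 12 |
| 36 | 36 | 30 |

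Months 1 and 3 hold prostate toxicity alone. From month 6 every row can hold both. The month-9 row combines effects nine months after the prostate course with effects about three months after the start of the metastasis course.

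**3. Does timing from each course separate the two?** Not by itself. With a 90-day boundary, the late period of the prostate course begins at about month 3 and stays open, so both periods of the metastasis course fall inside it. An event at month 7 is at once late for the prostate course and acute for the metastasis course. Separation therefore also needs the organ system or the irradiated field.

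**4. Section 8.3 beside the safety rules.** Section 5.6 and the synopsis rule use patients as the unit and the end of irradiation as the origin, with 30- and 90-day marks. Section 8.3 uses the visit as its unit and states no origin per course.

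**The case against.** The strongest reply is that section 8.3 does not exclude a per-patient table. It says side effects will be described at each time point; it does not say that nothing else will be done. Because the synopsis timeline calls side effects secondary endpoints, the frequencies and confidence intervals in section 8.3 may well be meant to cover them. Worst-grade tables are also often specified in a statistical analysis plan, which is not at hand. This stands: a reader might infer that the share of men ever harmed will go unreported, but the protocol does not support that.

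It can also be said that counting by patient and by course already exists. Section 5.6 and the stopping rule define their own counts and do not depend on the table in section 8.3. Section 7.2 records side effects when irradiation begins and ends, and section 4.3.3 ties its later visits to the end of metastasis treatment. This too stands, so it would be wrong to conclude that the safety rules cannot be applied or that neither course can be read at all. But section 5.6 describes a look tied to the first third of patients, not a final summary.

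A further tempting step is numerical. Suppose five of 27 men each had one grade 3 episode seen at one of the 13 follow-up visits. The average visit-wise rate would be 5/27/13 = 1.4%, against 18.5% per patient (exact 95% CI 6.3 to 38.1%). One might then say that the planned table would pass as agreeing with section 4.3.2, where "the normal tissue constraints are chosen so that the risk of long-term side effects is 1-2" per cent. That comparison fails. The five men are assumed, and the protocol plans no average over visits. The 1-2% concerns long-term effects of metastasis irradiation, whereas the example spreads transient episodes over visits that include two before that course. Lasting effects would recur from visit to visit and would not be diluted in this way.

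What remains is narrower. The protocol does fix a method for side effects, and that method alone does not answer objective 3.

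**Conclusion.** The point holds as a modest one. Followed as written, the method that section 8.3 states for side effects yields prevalence at each visit. It does not determine the share of men ever affected: under an assumed constant 5% per visit over 14 visits, that share could be anything from 5% to 70%. From month 6 the rows overlay later prostate effects and early metastasis effects, while months 1 and 3 do not. Section 8.3 names neither a per-patient summary nor an origin for each course, although section 5.6 and the synopsis rule count patients from the end of irradiation.

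The protocol does not show that harm will be understated or that a per-patient figure will be withheld. The conclusion rests on the text of section 8.3 and the layout of Fig. 2; the prevalences are illustrations. The main toxicity summary should be corrected because side effects are a numbered objective. The sample size, the primary endpoint and its test are untouched.

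**What to change.** In section 8.3, add as the main toxicity summary the number and percentage of treated patients, with exact 95% confidence intervals, by worst CTCAE grade. Count only events that are new or worse than at the enrolment assessment already planned in section 7.2. Report the summary for an acute period (up to 90 days) and a late period (after 90 days), the boundary the protocol's safety rules already use. Time it from the end of prostate irradiation and, separately, from the end of metastasis irradiation, each among the men who received that course.

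For events after month 6, assign the course by organ system or irradiated field, and report those that cannot be assigned, such as pelvic events where pelvic metastases were also treated, as a category of their own. Keep the visit-wise tables and plots as supportive. Cumulative incidence of the first event is optional in 27 men.

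The cost is a few lines of text, a little more programming and a rule for assigning events, on CTCAE records and irradiation data already planned for collection. The reported toxicity figure will look less favourable than visit-wise rates. No dose, visit or stopping rule needs to change for this.

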	
 
- other active tumor disease in the last 2 years (except basal cell carcinoma of the skin/melanoma in remission)
 
- Zn TUR-P or HIFU less than 6 months before RT start, Zn surgical resection of the prostate
 
- Pre-irradiation in the pelvic area
 
- Serious pre-existing conditions affecting the bladder or rectum (e.g., active fistula, chronic inflammatory bowel disease)
 
- Presence of a tumor predisposition syndrome
 
- serious pre-existing urological conditions
 
- Contraindications to performing a PSMA-PET/CT scan
 
- Contraindications to performing a Radiation
 
- Pre-irradiation, which involves ablative irradiation of the Metastases prevented
 
- In T4 stage: Persistent infiltration of the rectum- Mucosa after 6 months of systemic therapy; in Bladder infiltration: critical evaluation
 
- Rising PSA level between initial diagnosis and Study screening
 
- Indication to change systemic therapy or Initiation of chemotherapy before the start of the study
 

Description of the Medical Product/Medical Device	-
Study Design:	
Current: Pilot study (single-arm phase II study, Fleming design)
 
Therapeutic intervention:
 
 
1. Stereotactic radiation of the primaries (5 x 7.25 Gy, Alternatively, moderate according to departmental standard Hypofractionation with 20 x 3.0 Gy or 6 x 6.0 Gy analogously Stampede possible)
 
2. Stereotactic radiotherapy during systemic therapy continuing metabolically active metastases (residual) Metabolic activity in PSMA-PET/CT; ablative radiotherapy (stereotactic or normofractionated) in patients with primarily non-visceral metastatic adenocarcinoma of the prostate
 
 
Anti-androgen systemic therapy following urological Standard of Care

Length of study/ Timelines	Total trial duration: 36 months

	
Duration for individual patient: Study treatment: 2 to 6 weeks
 
Follow-up: 36 months
 
Number of visits: 15 visits
 
FSI (First Subject In): 12/2025
 
LSI (Last Subject In): 12/2026
 
LSO (Last Subject Out): 06/2027
 
DBL (Data Base Lock): 03/2029 (primary endpoint)
 
06/2030 (secondary endpoints (QoL, side effects))
 
Statistical Analyzes Completed: 06/2029
 
Trial Report Completed (primary endpoint): 12/2029

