#### 3.2 Secondary endpoints

- PSA progression
- Lesion-specific response of irradiated lesions in PSMA-PET/CT
- Objective response rate (ORR)
- Interval until changing systemic therapy
- Overall Survival (OS)
- Failure-free survival (FFS) as the primary outcome of any disease specific event
- Progression-free survival (PFS)
- Metastasis-free survival (MFS)
- Disease-specific survival (prostate cancer specific survival, PCS)

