# 6. Guidelines for radiotherapy

## 6.1 Specifications for systemic therapy (antihormonal therapy according to guidelines)

In accordance with the S3 guideline, the initiation of systemic antihormonal therapy is started six months prior to study screening by the treating urologists (either at a center or in private practice). This involves complete androgen blockade through a combination of ADT and NHT (e.g., apalutamide, enzalutamide, or others, as determined by the primary treating urologist). The choice of drug and NHT is determined by the tumor board or the primary treating urologist, in accordance with the S3 guideline. This is the standard therapy and not part of the study protocol presented here. When initiating long-term hormone therapy, each patient is offered radiation gynecomastia prophylaxis according to departmental standards. Systemic therapy should be initiated at least six months prior to study enrollment and the PSMA-PET/CT scan.

If the PSA level does not fall completely to  $<0.2$  ng/ml and thus the study inclusion criteria are met, systemic therapy will be continued until a significant PSA increase occurs (doubling of the baseline value or PSA doubling time of  $< 6$  months).

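### Kaplan-Meier is prescribed for time to change of systemic therapy, although death before a change is a competing event; a cumulative incidence estimator should replace it (small effect, secondary endpoint)

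*Protocol*

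**What the plan says.** Section 8.3 first promises descriptive statistics with 95% confidence intervals for all primary and secondary endpoints. It then turns to the time-to-event group, "For endpoints that represent an interval until an event (progression-free survival, time to change of systemic therapy, overall survival"), and says that "an evaluation is also performed using Kaplan-Meier curves and log-rank tests". Cox regression is added for influencing factors. No competing-risk method appears in the protocol.

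The endpoint is listed in Section 3.2 and the Synopsis simply as "Interval until changing systemic therapy". It is not limited to progression, and death is not part of it. The protocol does not say whether a death before any change is an event, a censoring or a competing event.

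Four other places bear on the point:
- Section 3.3, objective 2, expects benefit from treating all active lesions, "as this should prolong the interval for changing systemic therapy".
- The exploratory endpoints include "Reason for changing systemic therapy".
- Section 6.1 states that "systemic therapy will be continued until a significant PSA increase occurs".
- The Synopsis gives "Follow-up: 36 months" per patient.

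**The concern.** Kaplan-Meier treats a censored patient as still able to have the event later. That suits a man whose follow-up ends while he is on first-line therapy, but not one who has died on it. If deaths are censored, the complement of the curve describes a hypothetical cohort in which nobody dies first, and it exceeds the proportion of enrolled men who change therapy.

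Counting death as an event would remove this bias, but the curve would then show time to change or death, which is not the endpoint in Section 3.2. So the named estimator and the listed endpoint do not fit each other under either treatment of death.

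Death is a real possibility here. Men up to 85 years and ECOG 2 are eligible, follow-up is 36 months, and Section 2.1 links the insufficient PSA decline required for entry to poorer survival. At stake is the accuracy of one secondary endpoint that objective 2 relies on, together with PSA, PFS and OS. The decision on the trial's success is not at stake.

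**Working it through.** **The plan's own figure.** The protocol states no figure for this endpoint. The sample size, used below only for precision, reproduces: with 27 patients and success at 8 or more responders, the exact one-sided alpha at a 15% response rate is 0.0398 and power at 40% is 0.9047.

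**Inputs**
- Horizon: 36 months (Synopsis).
- F, the 36-month Kaplan-Meier probability of any change with deaths censored: not given; assumed 30%, 50% and 70%.
- d, the 36-month probability of death implied by the death rate among men who have not changed therapy: not given; assumed 2%, 5% and 10%. The upper values are 19% and 27%, from the only overall survival percentages in the protocol: three-year OS of 81% and 73% in the cited randomised phase 3 trial of prostate radiotherapy (Section 2.2).

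The 40% two-year figure in Sections 2.4 and 4.1 is not used as a rate of change. It describes freedom from recurrence or progression, and Section 4.1 says repeat irradiation delayed the switch of systemic therapy.

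**Formulas** (constant hazards, cumulated over 36 months)
- Change: a = −ln(1 − F). Death without change: b = −ln(1 − d).
- Deaths censored: 1 − KM = 1 − exp(−a) = F.
- Death competing: CIF = a/(a + b) × [1 − exp(−(a + b))] = a/(a + b) × [1 − (1 − F)(1 − d)].
- Excess = F − CIF.

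**Worked example**, F = 50%, d = 5%: a = 0.6931 and b = 0.0513. CIF = 0.6931/0.7444 × (1 − 0.50 × 0.95) = 0.931 × 0.525 = 0.489. The excess is 1.1 points.

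**Results** (CIF, with excess in points)

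| d | F = 30% | F = 50% | F = 70% |
|---|---|---|---|
| 2% | 29.7% (0.3) | 49.6% (0.4) | 69.4% (0.6) |
| 5% | 29.3% (0.7) | 48.9% (1.1) | 68.6% (1.4) |
| 10% | 28.6% (1.4) | 47.7% (2.3) | 67.1% (2.9) |
| 19% | 27.2% (2.8) | 45.6% (4.4) | 64.4% (5.6) |
| 27% | 26.0% (4.0) | 43.7% (6.3) | 61.9% (8.1) |

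The last row lets men still on first-line therapy die at the full all-cause rate behind the cited trial's 27%. In its last cell, 78.1% − 61.9% = 16.2% of men die before a change. Requiring 27% of all enrolled men to die before any change would be harsher. It needs b of about 0.58, so CIF = 1.204/1.784 × (1 − exp(−1.784)) = 0.675 × 0.832 = 56.2%, an excess of about 14 points. That death rate is about 1.8 times the cited trial's (0.58/0.315), so I leave it outside the range.

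**Sampling error.** The 95% half-width for a proportion with n = 27 is 1.96 × √(0.5 × 0.5/27) = 18.9 points at 50%, and 17.3 points at 30% or 70%. Every excess above is smaller.

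**The case against.** The strongest reply is that the protocol never says deaths are censored. Event and censoring rules are commonly left to the SAP, which is not at hand, and Kaplan-Meier would be valid for a composite with death. This stands as far as censoring is an inference from standard practice. It does not remove the point: the estimator is already fixed, the endpoint is already listed without death, and a composite would be a different endpoint.

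Second, Section 8.3 also plans absolute and relative frequencies, so a crude proportion would appear beside the curve. With complete follow-up that proportion equals the cumulative incidence. This helps only while nobody is lost or administratively censored, and the report could then carry two different figures for one quantity.

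Third, the bias is small, deaths often follow a change prompted by progression, and no decision rests on this endpoint. All of that stands.

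A reader might go further in three ways that the protocol does not support:
- That the planned curve claims to show change because of progression. The listed endpoint is change for any reason, so counting every change follows its definition.
- That the reason for change goes unused. It is an exploratory endpoint in its own right; it is only not linked to the time-to-change analysis. Putting a number on changes made for tolerability would need a share that the protocol does not give.
- That Kaplan-Meier is prescribed for prostate-cancer-specific survival. Section 3.2 lists "Disease-specific survival (prostate cancer specific survival, PCS"), but the parenthesis in Section 8.3 does not name it.

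**Conclusion.** The point holds as a mismatch between estimator and endpoint on one secondary endpoint. If deaths before a change are censored, the error runs in one direction: the reported probability of change is too high. Its likely size is about 0.3 to 1.4 points at 2% to 5% death without change. It is about 8 points at the upper end, where men on first-line therapy die at the cited trial's full rate and the Kaplan-Meier probability of change is 70%.

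These figures rest on constant hazards and on assumed event probabilities; only the survival figures of 73% and 81% come from the protocol. They are from men with a limited number of metastases, so 8 points is the top of the range examined and not a strict bound. Sampling error with 27 patients is larger throughout. The case for changing the text is that the bias is systematic and costs almost nothing to avoid.

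**What to change.** In Section 8.3, take time to change of systemic therapy out of the Kaplan-Meier group. State that it will be described by the Aalen-Johansen cumulative incidence of any change of systemic therapy, with death without change as a competing event and 95% confidence intervals. PFS and OS include death by their usual definition and can stay under Kaplan-Meier. Log-rank and Cox analyses of time to change can also stay if they are described as analyses of the cause-specific hazard.

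As a supportive analysis, because objective 2 concerns disease control and the reason for change is already collected, report the cumulative incidence of progression-driven change, with change for other reasons and death as competing events. If prostate-cancer-specific survival is analysed as time to event, use the same estimator with other-cause death competing.

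The cost is a change of analysis wording and slightly more analysis work. No new data are needed, since reason for change, survival and cause-specific survival are already listed for collection. The downside is little precision: with 27 patients the progression-driven curve in particular will be wide and should be read as descriptive.
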